#### 8.1.5 Maximum Tumor Thickness by B-scan Ultrasound

Descriptive statistics for change from baseline in maximum tumor thickness as measured by B-scan ultrasound in the study eye will be summarized at each visit by cohort, overall and for subgroups (defined in Section 4.4).

#### 8.1.6 Largest Basal Diameter by Fundus Photography

Descriptive statistics for change from baseline in largest tumor basal diameter as measured by color fundus photography in the study eye will be summarized at each visit by cohort, overall and for subgroups (defined in Section 4.4).

#### 8.1.7 Tumor Reponse by B-scan Ultrasound and Largest Basal Diameter by Fundus Photography

Number and percentage of subjects with tumor control (PR and SD) on both tumor thickness and LBD and tumor progression on either tumor thickness or LBD in the study eye will be summarized at each visit by cohort, overall and for subgroups defined in Section 4.4. Definitions in Section 8.1 will be used.

#### 8.1.8 Tumor thickness growth rate

Tumor thickness growth rates after treatment will be compared to historical growth rates in subjects with documented growth and other subgroups defined in section 4.4 using a mixed model repeated measures (MMRM) analysis. These analyses will be provided in a separate report by the sponsor.

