The intention is to alternate the enrolment of Cohorts 10 and 11. If during the enrollment of these subjects, a subject has just been enrolled into Cohort 11 and a subject with documented growth presents, then that subject may instead be enrolled into Cohort 11 rather than Cohort 10 for which they would not be eligible due to the presence of documented growth and instead will be assigned to receive the first of 2 cycles of AU-011.

If 2 subjects experience a DLT during treatment with Cycle 2, as defined in Section 8.4.1., then no further subjects will receive Cycle 2 of AU-011 until discussed with the independent ocular oncologist and medical monitor and continuation of enrollment is confirmed.

Subjects with Documented Growth

Enrollment in Cohorts 10 and 11 was closed following approval of protocol revision 11 (Rev-11) at each site. An additional cohort, Cohort 12, of subjects with minimum defined levels of documented growth will be initiated to allow assessment of safety and efficacy of 2 cycles of AU-011 treatment in this key subgroup of subjects with CM. Since Cohort 12 has the same dose as Cohort 11 no safety review will be required.

Up to 15 subjects, who meet the criteria for a clinical diagnosis of CM with documented growth as defined in Inclusion Criteria 5C, will enter Cohort 12 and receive two cycles of AU-011 treatment (each cycle will be comprised of 3 repeat 80 µg doses, each followed by 2 repeat laser applications). Cycle 2 of AU-011 will be administered as 3 repeat 80 µg doses, each followed by 2 repeat laser applications no earlier than the Week 12 Visit and after resolution of any inflammation resulting from the first cycle or when the inflammation is minimal and decreasing based on investigator judgement. Cycle 2 should be administered as soon as reasonably possible after inflammation has resolved or is minimal and decreasing based on investigator judgement. If the fovea is near the tumor edge, an adjustment to the laser procedure should be performed on each treatment day of both cycles as outlined in section 8.2.2 and the Injection and Laser Procedure Manual.

If 2 subjects experience a DLT during treatment with Cycle 2, as defined in Section 8.4.1., then no further subjects will receive Cycle 2 of AU-011 until discussed with the independent ocular oncologist and medical monitor and continuation of enrollment is confirmed.

Study Methods

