7.1. Subject Inclusion Criteria

Subjects must:

- 1. Be at least 18 years of age of either gender or any race.
- 2. Have been informed about the nature and requirements of the study, voluntarily agreed to participate in the study, and documented this by signing the Informed Consent Form (ICF) before participating in any study-related activities.
- 3. Be willing and able to follow all instructions and attend all study visits.
- 4. Per the expert opinion of the Investigator, have clinically diagnosed primary CM with no known metastatic disease.
- 5. Have clinically diagnosed primary CM:
 - A. with tumor thickness of ≥ 1.2 mm and ≤ 3.0 mm on B-scan ultrasound and with a largest basal diameter of ≤ 13.0 mm on fundus photos associated with tumor growth,

OR

- B. with tumor thickness of ≥ 2.0 mm and ≤ 3.0 mm on B-scan ultrasound and with a largest basal diameter of ≤ 13.0 mm on fundus photos associated with the presence of subretinal fluid by OCT AND at least one of the following:
 - a. Overlying orange pigment (lipofuscin) on fundus photos
 - b. Vision loss
 - c. Flashes or floaters

OR

C. Criteria for Cohort 12: with tumor thickness of ≥ 0.5 mm and ≤ 3.0 mm on B-scan ultrasound, a largest basal diameter of ≤ 13.0 mm on fundus photos with an estimated tumor volume ≤ 50 mm³ associated with tumor growth within 2 years of screening (defined as ≥ 0.4 mm increase based on intersite measurements or ≥ 0.3 mm based on within site measurements on tumor thickness)

NOTE: Whenever available at the investigative site or referring site, historical images (B-scans and/or color fundus photos) for all subjects should be provided to the Independent Reading Center at the time of entry to the study. The investigative site should make all reasonable efforts to obtain this information from referring sites.

- 6. In the opinion of the treating physician, the subject could be managed by interventional therapy, or by cautious observation.
- 7. Be treatment-naïve for their primary CM.

- 8. Have a tumor for which the entire extent must be able to be imaged on required fundus photography in a single frame and treated by the laser.

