10.5. Efficacy

Since this is a single arm, exploratory study, no formal hypothesis testing will be performed. Efficacy will be assessed at the Week 12, 26 39, 52, 78 and 104 visits for any potential tumor response and changes in ETDRS best corrected visual acuity (BCVA). This will include change from baseline at each visit in tumor thickness by ultrasound and largest basal diameter by digital fundus photography. The proportion of subjects who meet the definition of stable disease (do not meet the definition of disease progression) will also be reported for each visit using change in tumor thickness and for changes in largest basal diameter. Change from baseline in ETDRS BCVA at Week 12 and at each subsequent visit will include changes in letter score and the proportion of subjects who lose or gain 5, 10 or 15 letters.

Exploratory analyses will be performed for change in internal reflectivity of tumors by A-scan ultrasound at each visit and macular changes (foveal avascular zone and vessel density) by OCTA at each visit.

Background and demographic characteristics will be presented. Continuous variables will be summarized by descriptive statistics (sample size, mean, standard deviation, median, minimum and maximum). Discrete variables will be summarized by frequencies and percentages.

Efficacy and safety will be analyzed at various intervals after the first 2 cohorts have completed 12 months of follow-up and then at further intervals as subsequent cohorts reach similar milestones. Specific details of the timing of such analyses will be included in the Statistical Analysis Plan.

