## 4.4 Subgroup Definitions

The following subgroups are defined for additional characterization of efficacy and/or safety of AU-011:

- Subjects with documented growth (DG): defined as subjects who had any amount of documented growth on tumor thickness
- Phase 3 Eligible (Ph3 Elig): defined as subjects with entry criteria similar to planned phase 3 criteria
  - Subjects with tumor thickness of  $\geq 0.5$  mm and  $\leq 3.0$  mm on B-scan ultrasound, a largest basal diameter of  $\leq 13.0$  mm on fundus photos with an estimated tumor volume  $\leq 50$  mm^3 and tumor growth of  $\geq 0.3$  mm on tumor thickness within 2 years of screening
- Phase 3 Eligible Therapeutic Regimen at 2 cycles (Ph3 Elig TR2C)
  - Phase 3 Eligible subjects who received 2 cycles of AU-011 treatment, each cycle comprised of three weekly treatments with 80 $\mu$ g x 2 laser applications
- Phase 3 Eligible - High Risk for Vision Loss (Ph3 Elig HRVL)
  - Phase 3 Eligible subjects with tumor  $\leq 3.0$  mm from the fovea or optic disc

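### The growth-rate comparison in SAP 8.1.8 is uncontrolled and made in subgroups picked for past growth, so regression to the mean alone will make growth appear to slow.

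*SAP*

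**What the plan says.** SAP 8.1.8 is two sentences long. The first sets the comparison: "Tumor thickness growth rates after treatment will be compared to historical growth rates in subjects with documented growth and other subgroups", by MMRM. The second defers it: "These analyses will be provided in a separate report by the sponsor". The SAP does not say which scans make up the historical rate, how the model is built, or whether one scan can enter both rates.

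The subgroups come from SAP 4.4, and all four require observed past growth in thickness:

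- Documented growth (DG) is "defined as subjects who had any amount of documented growth on tumor thickness".
- Phase 3 Eligible requires growth of at least 0.3 "mm on tumor thickness within 2 years of screening". Its two-cycle and high-risk-for-vision-loss subsets inherit that rule.

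The Cohort 12 entry rule in Protocol 7.1 separates two sources of measurement, "defined as ≥ 0.4 mm increase based on intersite measurements or ≥ 0.3 mm based on within site measurements on tumor thickness". The SAP subgroups make no such distinction.

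The note in Protocol 7.1 asks that, where available, "historical images (B-scans and/or color fundus photos) for all subjects should be provided to the Independent Reading Center". This makes the subjects' own pre-treatment rates the natural reading of historical, although SAP 8.1.8 does not say so.

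Protocol 10.5 describes the design: "Since this is a single arm, exploratory study, no formal hypothesis testing will be performed".

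**The concern.** The variable that puts a subject into the subgroup is also the before side of the comparison. A subject qualifies because a later scan read thicker than an earlier one. That difference is true growth plus the error of two scans, and choosing subjects on a large difference favours those whose errors happened to add. The historical rate is then too high on average, while later scans carry fresh error and return to the true rate. If a subject's true rate also varies over time, the same happens without any measurement error.

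A second effect arises if the qualifying scan also starts the post-treatment slope. That scan tends to read high, which pulls the post-treatment slope down.

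Efficacy in subjects with documented growth is a secondary objective, and Protocol 4.6 describes Cohort 12 as similar to the planned Phase 3 population. SAP 8.1.8 is the only place where the SAP sets treated growth against untreated growth. What is at stake is the interpretation of that estimate, and any use of it in planning. Moving the analysis to a separate report leaves the selection in place.

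**Working it through.** **Figures in the plan.** The documents give no growth rate, measurement SD, effect size or sample size for this analysis, so there is no stated figure to reproduce. The check asks what the comparison shows when treatment has no effect.

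**Inputs from the documents**
- Selection thresholds: c = 0.3 mm (Phase 3 Eligible) and c = 0 (DG), from SAP 4.4.
- Post-treatment scans at Weeks 12, 26, 39 and 52, from the protocol schedule.

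**Assumptions not in the documents**
- True growth rate has mean 0.2 mm/year and between-subject SD τ of 0.1 or 0.2.
- Per-scan error SD s is 0.05 to 0.20 mm, independent between scans.
- One historical scan lies T = 1 or 2 years before the qualifying scan.
- A least-squares slope stands in for the unspecified MMRM.

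The only document figure near measurement error is the 0.15 mm minimum detectable increase in Protocol 8.3.4. If read as 1.96·√2·s, it gives s = 0.15/2.77 = 0.054 mm. That reading is also an assumption.

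**Formulas.** The observed historical increase D is normal with mean 0.2T and SD σ = √(τ²T² + 2s²). With z = (c − 0.2T)/σ and λ = φ(z)/[1 − Φ(z)], the means among selected subjects are:
- observed historical rate = (0.2T + σλ)/T
- true rate = 0.2 + τ²Tλ/σ
- error in the qualifying scan = s²λ/σ
- post-treatment slope = true rate − 0.78 × (error in the qualifying scan) if that scan is the first of the five points; otherwise it equals the true rate.

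The 0.78 is the least-squares weight on a scan at time 0 with the other four at Weeks 12 to 52.

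**Worked case: c = 0.3, T = 1, τ = 0.2, s = 0.10**
1. σ = √(0.04 + 0.02) = 0.245; z = 0.1/0.245 = 0.408; λ = 1.075.
2. Observed historical rate = 0.2 + 0.245 × 1.075 = 0.463 mm/year.
3. True rate = 0.2 + (0.04/0.245) × 1.075 = 0.375 mm/year.
4. Error in the qualifying scan = (0.01/0.245) × 1.075 = 0.044 mm.
5. Shared scan: slope = 0.375 − 0.78 × 0.044 = 0.341; apparent slowing = 1 − 0.341/0.463 = 26%.
6. Scan not shared: 1 − 0.375/0.463 = 19%.

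A simulation with no treatment effect (600,000 subjects per scenario) gave 0.463, 0.376 and 0.341 for this case.

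**Apparent slowing with no treatment effect, over τ 0.1 to 0.2 and s 0.05 to 0.20**

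| Rule and history | Qualifying scan shared | Not shared |
|---|---|---|
| ≥ 0.3 mm, 1 year | 8–75% | 6–54% |
| ≥ 0.3 mm, 2 years | 2–42% | 1–23% |
| Any growth, 1 year | 3–48% | 2–35% |
| Any growth, 2 years | 1–20% | under 1 to 11% |

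The upper end of each row is τ = 0.1 with s = 0.20. For the first row, not shared, it is 1 − 0.234/0.506 = 54%.

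**Rates that vary over time.** With correlation 0.5 between a subject's past and future true rate (c = 0.3, T = 1, τ = 0.2), the apparent slowing is 27% even when s = 0.

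**The case against.** The strongest reply concerns size. For a static tumour that nevertheless qualified at 0.3 mm, the expected false growth is 0.35 mm (s = 0.1) to 0.45 mm (s = 0.2), and a reader might take that as the bias in this trial. The documents do not support that. The figure must exceed 0.3 mm by construction, and only 1.7% (s = 0.1) to 14% (s = 0.2) of static tumours would qualify. The trial enrols tumours that may truly be growing, and with precise scans over 2 years the slowing is only a few percent.

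A reader might also infer that both sides of the comparison are biased. That needs a shared scan. SAP 4.6 takes the last assessment on or before Day 1 as baseline, and Protocol 10.1.3 repeats the B-scan at Visit 2 unless it falls within 7 days of Visit 1. Sharing is therefore possible but not confirmed.

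The plan has some protections. The Cohort 12 rule is stricter for intersite measurements, at least two readers review screening B-scans (Protocol 6.1), and reader values are averaged (SAP 8). These reduce reader error, not error in acquiring the scan, and the intersite rule is not carried into SAP 4.4.

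It is also fair that the model is unseen and that historical could mean external rates. In that case the problem would be comparability instead. With no formal test planned, type I error is not at issue.

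These points limit the size. They do not change the direction or supply the missing specification.

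**Conclusion.** The concern holds as a bias of known direction and unknown size. If SAP 8.1.8 is followed on the subjects' own historical rates, it favours the drug whenever scans carry error or true rates vary over time. Under the stated assumptions the apparent slowing runs from about 1% to 75%. The 0.3 mm rule over a 1-year history is the most exposed, and the any-growth rule over 2 years the least.

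This does not show that any slowing the sponsor reports is wholly artefact. Nor would changing the population give an unbiased comparator. Inclusion criteria 5A and 5C select on growth, so the ITT population is still partly growth-selected. Cohort 10 is planned at about 6 subjects, was enrolled without documented growth, and leaves observation when growth is observed.

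**What to change.** Amend SAP 8.1.8, and carry the same text into the separate report:

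1. Define historical as the subject's own pre-treatment B-scans, and fit one piecewise mixed model with a slope change at first treatment.
2. Keep the scan that qualified the subject for growth out of the post-treatment slope. Give the post-treatment segment its own level, because a line forced to be continuous at treatment would let that scan's error back in. In the worked case this cuts the zero-effect slowing from 26% to 19%; with τ = 0.1 and the same s it falls from 47% to 34%. Bias therefore remains, and items 3 and 4 are still needed.
3. Beside the growth-selected subgroups, report the same model in all treated subjects with at least two historical B-scans, whatever growth they show. State that criteria 5A and 5C still select some of them on growth.
4. Report a simulated zero-effect benchmark over a range of measurement errors next to the estimate, and label the comparison as uncontrolled.

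Cohort 10 growth before treatment may be shown as context, not as a matched control.

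The cost is SAP wording, extra analysis of data already collected, a slightly less precise post-treatment slope, and probably a smaller estimated reduction. SAP v5.0 followed the first database lock, so the additions should be dated and described as made after it. Replacing the lead subgroups with the wider set is not proposed, since it would move the analysis away from the stated objective.

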### 8.2 Best Corrected Visual Acuity by ETDRS Protocol

The BCVA score or visual acuity score using the Early Treatment of Diabetic Retinopathy Study (ETDRS) protocol will be determined for each subject in each eye at each visit. The observed visual acuity score in the study eye will be used for the analyses.

Descriptive statistics for visual acuity score as well as for change from baseline in visual acuity score will be presented for each visit up to the Week 52 visit and at the end of study visit by cohort, overall and for subgroups (defined in Section 4.4).

Number and percentage of subjects with a 5, 10 or 15 letter gain or loss at each visit up to the Week 52 visit and at the end of study visit will also be included by cohort and overall. Number and percentage of subjects with visual acuity preservation (ie, not meeting visual acuity failure criteria as defined below) over 52 weeks will also be included overall and for subgroups (defined in Section 4.4).

Visual acuity failure is defined as having a  $\geq 15$  letter loss at Week 39 or Week 52 confirmed at the next visit excluding visits occurring post-SOC. Additional details are provided below:

- A  $\geq 15$  letter loss at Week 39 and confirmed at Week 52 (or at the next visit after Week 52 with non-missing data [regardless of the visit windowing algorithm as described in Section 4.1.2] if the subject's visual acuity data is missing at the Week 52 visit or the Week 52 visit did not occur). The data after a subject receives standard of care (SOC) is excluded (i.e., censored) from determination

Confidential

of visual acuity failure. If there is no subsequent confirmatory visit data is available after Week 39 then the subject is counted as a visual acuity failure.

- If the subject does not meet the  $\geq 15$  letter loss criterion at Week 39 but does meet the  $\geq 15$  letter loss criterion at Week 52, then the subject's next visit after Week 52 with non-missing data (regardless of the visit windowing algorithm as described in Section 4.1.2) will be the confirmatory visit (i.e., the subject will be counted as a visual acuity failure if the subject's confirmatory visit also is a  $\geq 15$  letter loss). The data after a subject receives standard of care (SOC) is excluded (i.e., censored) from determination of visual acuity failure. If there is no subsequent confirmatory visit data is available after Week 52 then the subject is counted as failure.
- If SOC occurs before Week 39, the subject's 2 most recent visits available before SOC (with non-missing visual acuity data), regardless of the visit windowing algorithm as described in Section 4.1.2, will be used. If both visit assessments indicate the loss is  $\geq 15$  letters at this visit the subject will be counted as a visual acuity failure, otherwise the subject will not be counted as a visual acuity failure.
- If both Week 39 and Week 52 visits are missing, the subject's 2 most recent visits before Week 39 (and before receiving SOC), regardless of the visit windowing algorithm as described in Section 4.1.2, with non-missing values will be used. If both visit assessments indicate the loss is  $\geq 15$  letters the subject will be counted as a visual acuity failure, otherwise the subject will not be counted as a visual acuity failure.
- If a subject does not have any post-treatment visual acuity data, the subject will not be counted as a visual acuity failure.

An additional summary of the following two tables including just site 009 (i.e., the site excluded from the Efficacy Evaluable Population) will be performed:

- Summary of Best Corrected Visual Acuity (ETDRS Letters) and Change from Baseline by Visit
- Number and percentage of subjects with visual acuity preservation (i.e., as defined above)

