7.3.3. Early Subject Termination or Subject Withdrawal

Subjects who discontinue from the study early for any reason will be asked to undergo Week 104/Early Termination assessments. If termination occurs before Visit 11 (Week 12), then all ophthalmic assessments, **including imaging** should be performed on both eyes at the Early Termination Visit.

All subjects who discontinue from the study early will be followed for up to 30 days after their last administration of study medication for the development of new AEs.

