## 11.2 Definition of Visit Windows in Reporting

The definition of visit label and visit windows in reporting are described in the table below.

Study Period	Visit Label	Definition [Day window]
Screening	Visit 1	= Subject screening date; nominally 1 to 28 days prior to the first AU-011 treatment. 'Day 1' - 'Date of assessment' = [1 to 28]. Alternatively, this is the assessment before the first treatment date.
Active Period	Visit 2 - D1 (Baseline)	= An assessment with the same date as recorded on the Day 1 Administration CRF Target date = 1
	Visit 3 - D2	= An assessment where 'Date of assessment' - 'Day 1' + 1 = 2 Target date = 2
	Visit 4 - D8	= An assessment where 'Date of assessment' - 'Day 1' + 1 = [8 - 9] Target date = 8
	Visit 5 - D9	= An assessment where 'Date of assessment' - 'Day 1' + 1 = [9 - 10] Target date = 9. Alternatively, this is the assessment one day after Visit 4 - D8.
	Visit 6 - D15	= An assessment where 'Date of assessment' - 'Day 1' + 1 = [15 - 16] Target date = 15
	Visit 7 - D16	= An assessment where 'Date of assessment' - 'Day 1' + 1 = [15 - 17] Target date = 16. Alternatively, this is the assessment one day after Visit 6 - D15.
Follow-up Period	Visit 8 - D29	= An assessment where 'Date of assessment' - 'Day 1' + 1 = [22 - 36] Target date = 29
	Visit 9 - W6	= An assessment where 'Date of assessment' - 'Day 1' + 1 = [37 - 50] Target date = 43
	Visit 10 - W8	= An assessment where 'Date of assessment' - 'Day 1' + 1 = [51 - 64] Target date = 57
	Visit 11 - W12	= An assessment where 'Date of assessment' - 'Day 1' + 1 = [65 - 113] Target date = 85
	Visit 12 - W26	= An assessment where 'Date of assessment' - 'Day 1' + 1 = [155 - 211] Target date = 183
	Visit 13 - W39	= An assessment where 'Date of assessment' - 'Day 1' + 1 = [246 - 302] Target date = 274
	Visit 14 - W52	= An assessment where 'Date of assessment' - 'Day 1' + 1 = [337 - 393] Target date = 365
End of Study	Visit 15 - W78	= An assessment where 'Date of assessment' - 'Day 1' + 1 = [463 - 631] Target date = 547
	Visit 16 - W104	= An assessment where 'Date of assessment' - 'Day 1' + 1 = [700 - 756] Target date = 728

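### A first 15-letter loss at a subject's last visit is a visual acuity failure at Week 39 or Week 52, but preserved vision before Day 246 or on Days 303 to 336 (SAP 8.2)

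*SAP*

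**What the plan says.** SAP 8.2 reports the number and percentage of subjects with "visual acuity preservation (ie, not meeting visual acuity failure criteria as defined below) over 52 weeks", overall and for subgroups. Failure is a loss of at least 15 letters, in the SAP's words a "letter loss at Week 39 or Week 52 confirmed at the next visit excluding visits occurring post-SOC". Further bullets settle the cases where data are missing.

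- **Loss at Week 39, nothing later:** "If there is no subsequent confirmatory visit data is available after Week 39 then the subject is counted as a visual acuity failure".
- **Loss first seen at Week 52, nothing later:** "If there is no subsequent confirmatory visit data is available after Week 52 then the subject is counted as failure".
- **Neither named visit available:** "If both Week 39 and Week 52 visits are missing, the subject's 2 most recent visits before Week 39" are used, leaving out acuity after standard of care. If both show a loss of at least 15 "letters the subject will be counted as a visual acuity failure, otherwise the subject will not be counted as a visual acuity failure".
- **Standard of care before Week 39:** the last two acuity visits before that treatment are used, and again both must show the loss.

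SAP 11.2 defines Week 39 as "Date of assessment' - 'Day 1' + 1 = [246 - 302] Target date = 274" and Week 52 as Days 337 to 393. Under SAP 4.1.2 an early withdrawal visit can stand in for a missing scheduled visit only if it falls inside that visit's window. Protocol 7.3.3 provides for an exit examination: "Subjects who discontinue from the study early for any reason will be asked to undergo Week 104/Early Termination assessments". Protocol 10.1.17 includes acuity in it.

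**The concern.** The same observation, a new loss of at least 15 letters as the last value on record, is classified in opposite ways according to the day on which it was measured. At the two named visits the SAP resolves missing confirmation against the treatment. Before Week 39 it resolves it in favour of the treatment. Between the two windows it makes no provision at all.

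Preservation is defined as not meeting the failure criteria, and ITT, the primary efficacy population (SAP 4.3.1), contains every enrolled subject. A subject who falls through the criteria therefore stays in the denominator and is counted as a success. The effect runs in one direction only. Vision sparing is central to the rationale for this treatment (Protocol 4.6), and subjects who leave with new vision loss are those for whom the handling of missing data matters most. SAP 8.3 and the table list in SAP 11.3.1 plan no preservation analysis under any other handling of missing confirmation.

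**Working it through.** The plan gives no expected preservation rate, dropout rate or sample size calculation for this endpoint, so there is no figure of its own to reproduce. The check applies the rules to test cases and then sizes the effect.

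**Inputs.** Failure bullets: SAP 8.2. Windows: SAP 11.2 (Week 39 = Days 246 to 302; Week 52 = Days 337 to 393). Substitution rule: SAP 4.1.2. Planned enrolment of about 60: SAP 3.3.

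**Step 1, the gap.** Days after the Week 39 window and before the Week 52 window: 337 − 302 − 1 = 34 days (Days 303 to 336).

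**Step 2, the rules applied.** In every row the last value shows a loss of at least 15 letters and no acuity follows.

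| Day of last value | Earlier acuity | Bullet reached | Result |
|---|---|---|---|
| 29, 43, 57, 85, 183 or 225 | no loss | both named visits missing | preserved |
| 274 | no loss | Week 39, no later data | failure |
| 320 | no loss, Week 39 present | none | preserved by default |
| 320 | no loss, Week 39 missed | both missing; looks only before Week 39 | preserved |
| 365 | no loss | Week 52, no later data | failure |
| 183, standard of care on Day 200 | no loss | standard of care before Week 39 | preserved |
| 225 | loss also on Day 183 | both named visits missing | failure |

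The last row shows the limit of the problem: a loss present at both of the last two visits before Week 39 is already a failure.

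**Step 3, size.** Let N be the denominator, F the other failures and k the subjects whose unconfirmed last loss is not counted.

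- SAP rate: (N − F)/N
- Rate if these subjects are failures: (N − F − k)/N
- Rate if they are excluded: (N − F − k)/(N − k)

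The first minus the second is k/N. With N = 60 and k = 1 this is 1/60 = 1.7 percentage points. F and k are not in the documents, so the values below are assumptions.

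| N = 60 | SAP | counted as failure, k = 1 / 3 / 6 | excluded, k = 1 / 3 / 6 |
|---|---|---|---|
| F = 6 | 90.0% | 88.3 / 85.0 / 80.0% | 89.8 / 89.5 / 88.9% |
| F = 12 | 80.0% | 78.3 / 75.0 / 70.0% | 79.7 / 78.9 / 77.8% |

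The SAP rate is the highest of the three in every cell. In a subgroup of size n the step is 1/n. Subgroup sizes are not given; an assumed n of 15 gives 1/15 = 6.7 points and an assumed n of 6 gives 1/6 = 16.7 points.

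**The case against.** The strongest reply is that the endpoint is confirmed loss. The SAP's change summary says the rule for two missing visits was revised in v5.0 for consistency with the overall definition. Treatment is expected to cause ocular inflammation, managed with steroids (Protocol 8.3.1), so an early dip may be transient. Asking for two concordant visits early, and taking the cautious default at the late target visits, is a reasonable design. This stands for exits before Day 246. It does not explain Days 303 to 336, where one route reaches no failure bullet and the other looks only at visits before Week 39.

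It is also fair that the trial's primary objective is safety, that nothing is tested formally, and that acuity is reported elsewhere. Listing 16.2.3 would show the loss. The 15-letter table may show it in its end-of-study column, depending on how that column is filled. Neither changes the preservation count.

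Several stronger readings are tempting, but the documents do not support them:

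- **The exit measurement is discarded.** Inside a named window it can stand in for the missing visit under the strict rule. Before Week 39 it is one of the two visits used and needs agreement from the visit before.
- **Baseline could serve as the second visit, so failure would be impossible.** The SAP is silent on this. With acuity scheduled on Days 2, 8, 15 and 29 and at Weeks 6, 8, 12 and 26, having a single post-treatment value should be rare.
- **Ignoring loss first seen after Week 52 is a fault.** The endpoint covers 52 weeks.
- **The late revision was made to favour the treatment.** It followed the first database lock, but the documents show neither its effect nor any reason other than consistency.

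**Conclusion.** The inconsistency is real and lies in the text of SAP 8.2. An unconfirmed last loss of at least 15 letters is a failure at Week 39 or Week 52. It counts as preserved vision before Day 246, under both the missing-visit bullet and the standard-of-care bullet. On Days 303 to 336 a first loss is never counted. The gap has no stated rationale and should be closed. The early two-visit rule is a defensible choice whose influence should be shown, so the documents do not support saying that it must be replaced.

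Each affected subject adds 1.7 points to the overall rate compared with counting a failure. This assumes a denominator of about 60. The total effect cannot be stated, because the documents give neither the number of such exits nor the reasons for them. A reader might quote 6.7 points for Cohort 12 at its maximum of 15 subjects. SAP 8.2 specifies preservation overall and for subgroups, not by cohort, so that figure only illustrates a small denominator.

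**What to change.** 1. **Close the gap in the main rule.** State in SAP 8.2 that, when Week 52 acuity is missing, a loss of at least 15 letters at a visit on Days 303 to 336 and before standard of care, with no later acuity to refute it, is a failure, as at Week 39 and Week 52. In the bullet for two missing visits, use the most recent visits up to Day 336. Apply the added sentence first, so that the two do not conflict.
2. **Keep the two-visit rule before Week 39 for the main analysis and show its influence.** Add a sensitivity row to Table 14.2.2.3 and to the site 009 table, 14.2.2.5. The row counts as a failure any unrefuted loss of at least 15 letters at the last available visit up to Day 393 and before standard of care. Report how many subjects it reclassifies.

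The cost is a few sentences in the SAP and two re-run tables, with no new data. In the sensitivity row a transient inflammatory dip at an early exit visit would count as a failure, so that rate may be slightly less favourable. Showing it beside the main row lets the reader judge.
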